- PSTEV and PSTC: Mann-Whitney U (likely non-normal); median difference with 95% CI

SAP-6. ADVANCED ANALYTICAL METHODS

SAP-6.1 Clinical Predictive Model for CSD

A **clinical predictive model** for CSD formation will be developed using **Firth penalized logistic regression**, justified by the ratio of events to variables approaching the threshold defined by Peduzzi et al.

Model development:

- Variable selection: univariate screening ($p < 0.20$) + a priori clinical variables
- Stability: **Bootstrap validation (10,000 replications)**
- Optimal threshold: **Youden Index**
- Internal validation: **10-fold cross-validation** and **70/30 data partition**
- Performance: AUC, sensitivity, specificity, positive and negative predictive values

SAP-6.2 Mediation Analysis

The **mediating role of CSD at 6 weeks** on the relationship between hysterorrhaphy technique and RMT at 6 months will be assessed using the **counterfactual mediation framework (Imai et al.)**.

Estimated quantities:

- **ACME** (Average Causal Mediation Effect): indirect effect through CSD at 6 weeks
- **ADE** (Average Direct Effect): direct effect of technique on RMT
- **Total Effect** and **proportion mediated**

Method: Bootstrap with **10,000 replications**

Sensitivity analysis: Critical ρ (rho) analysis to quantify robustness to unmeasured confounders

SAP-6.3 Inter-Operator Homogeneity

Breslow-Day test for homogeneity of treatment effects across operators (surgeons), to assess whether results are consistent regardless of the individual performing the procedure.

SAP-6.4 Measurement Reproducibility

Inter-observer concordance will be evaluated by **double-blind reading (n = 30 randomly selected examinations)**:

- Continuous variables (RMT, AMT): **Intraclass Correlation Coefficient (ICC)**
- Categorical variables (CSD presence): **Cohen's Kappa**

Temporal concordance of RMT measurements (6 weeks vs. 6 months):

- **Lin's Concordance Correlation Coefficient**
- **Bland-Altman analysis** (mean difference and limits of agreement)

SAP-7. SUBGROUP ANALYSES

Pre-specified subgroup analyses for the primary outcome (RMT at 6–7 months):

Subgroup Factor	Categories	Statistical Test
BMI category	< 30 vs. 30–34.9 kg/m ²	Interaction term in regression
Gestational age	37–38+6 vs. ≥ 39 weeks	Interaction term
Indication for CS	Labor dystocia vs. Fetal indication vs. Maternal indication	Interaction term
Uterine exteriorization	Yes vs. No	Interaction term

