11. SAMPLE SIZE CALCULATION

The sample size was determined based on the primary outcome — **RMT at 6 months** — using the standard formula for comparison of two independent means:

$$n = \frac{2 \times (Z_{\alpha/2} + Z_{\beta})^2 \times \sigma^2}{\Delta^2}$$

Parameters:

- Two-sided significance level: $\alpha = 0.05$ ($Z_{\alpha/2} = 1.96$)
- Statistical power: 80% ($Z_{\beta} = 0.842$)
- Conservative standard deviation: **$\sigma = 3.5$ mm**
- Minimum clinically meaningful difference: **$\Delta = 1.3$ mm**

Base sample size: 114 participants per group

Adjustment for loss to follow-up:

Based on local postpartum follow-up data and published literature, a **30% loss to follow-up rate** was anticipated:

$$n_{adjusted} = \frac{114}{1 - 0.30} \approx 163 \text{ per group}$$

Total enrolled: 384 participants (192 per group)

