8. ADVANCED ANALYSES

8.1 Clinical Predictive Model

Method: Firth penalized logistic regression (justified by Peduzzi events/variable threshold)

Validation: Bootstrap (10,000 replications) + 10-fold cross-validation + 70/30 split

Threshold: Youden Index

Performance: AUC, sensitivity, specificity, PPV, NPV

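### The CSD prediction model plans an inefficient 70/30 split and leaves open whether predictor selection is repeated in each resample and which AUC is the headline

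*SAP*

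**What the plan says.** SAP-6.1 plans a Firth penalized logistic model for CSD, "justified by the ratio of events to variables approaching the threshold" given in a cited source. It states no event count, number of candidate predictors or threshold value.

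Under model development it lists:
- variable selection by "univariate screening ($p < 0.20$) + a priori clinical variables";
- a bootstrap of 10,000 replications, labelled as a check of stability;
- a cut-off chosen by the Youden Index;
- internal validation by "10-fold cross-validation and 70/30 data partition";
- "Performance: AUC, sensitivity, specificity, positive and negative predictive values".

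Section 8.1 of the combined document puts all three methods under validation, "Bootstrap (10,000 replications) + 10-fold cross-validation + 70/30 split", and does not mention screening.

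Neither section says whether screening and the cut-off are redone in each bootstrap sample, fold or training part. Neither says whether the bootstrap is used to correct optimism, or which AUC is the main result. Identifying predictors of CSD is secondary objective 6 (protocol section 3.2), and a ROC curve for the model is a named figure in SAP-11.

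**The concern.** There are two separate points.

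**The split.** A method chosen because events are limited relative to variables is paired with a validation step that fits on 70% of the women and tests on the other 30%. The test part then holds few events, so its AUC is imprecise. Cross-validation and the bootstrap answer the same question using every woman.

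**Selection and the headline.** Choosing predictors by their p-values in the data at hand is part of model fitting. If it is done once on everyone and only the regression is refitted in each fold, the held-out women have already influenced the choice of predictors, and the validated AUC is too high. The same holds for sensitivity and specificity at a cut-off tuned and assessed on the same data. The plan yields an apparent, a bootstrap, a cross-validated and a split estimate and does not say which one leads. At stake is an overstated or poorly determined claim of how well CSD can be predicted.

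**Working it through.** **Inputs from the documents.** Enrolment is 384 and anticipated loss to follow-up is 30% (protocol section 11). Binary outcomes are analysed as complete cases (SAP-10). SAP-6.1 gives no figure to reproduce. The section that supplies the 30% does reproduce: 2 × (1.96 + 0.842)² × 3.5² / 1.3² = 113.8, so 114 per group, and 114 / 0.70 = 162.9, so 163. Enrolment of 384 exceeds 2 × 163 = 326; I use 384, which favours the plan. With 30% loss, 384 × 0.70 = 268.8, about 269 women.

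**Assumptions not in the documents.** CSD prevalence 15–40%; 12 or 20 independent candidates; four forced variables; either no true predictors or three with a log odds ratio of 0.35 per SD.

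**Step 1: precision of the split.** Events = N × prevalence; test set = 0.30 × N. The Hanley–McNeil variance with n₁ events and n₂ non-events is

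Var = [A(1−A) + (n₁−1)(q₁−A²) + (n₂−1)(q₂−A²)] / (n₁n₂), with q₁ = A/(2−A) and q₂ = 2A²/(1+A).

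At A = 0.70, q₁ = 0.5385 and q₂ = 0.5765. For N = 269 and 25% prevalence, the test set has 81 women, 20 of them events: Var = [0.21 + 19 × 0.0485 + 60 × 0.0865] / (20 × 61) = 0.00518, SE = 0.072, half-width 1.96 × 0.072 = 0.141. The same formula on all 269 women (67 events) gives 0.077.

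| N | Prevalence | Events, all | Events, test | 95% half-width, test | 95% half-width, all |
|---|---|---|---|---|---|
| 384 | 15% | 58 | 17 | 0.147 | 0.079 |
| 384 | 25% | 96 | 29 | 0.117 | 0.064 |
| 384 | 40% | 154 | 46 | 0.100 | 0.055 |
| 269 | 15% | 40 | 12 | 0.175 | 0.096 |
| 269 | 25% | 67 | 20 | 0.141 | 0.077 |
| 269 | 40% | 108 | 32 | 0.120 | 0.065 |

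The ratio is about 1.8 in every row, as expected from 1/√0.30 = 1.83.

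**Step 2: where screening is done.** Each simulated data set was screened at p<0.20, the four forced variables were added, and a Firth model was fitted. The true AUC was taken from 8,000 new subjects. There were eight settings: N = 384 at 25% prevalence and N = 269 at 15, 25 and 40%, each with 12 or 20 candidates, and 150 replicates per setting. Ranges are over the eight settings.

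| Estimate | No true predictors (true AUC 0.50) | Three weak predictors: difference from true AUC (0.604–0.635) |
|---|---|---|
| Apparent | 0.60–0.67 | +0.05 to +0.13 |
| 10-fold CV, screening once on all data | 0.53–0.57 | +0.01 to +0.05 |
| 70/30, screening once on all data | 0.53–0.58 | +0.01 to +0.04 |
| 10-fold CV, screening in each fold | 0.48–0.51 | −0.015 to −0.003 |
| 70/30, screening in training part only | 0.50–0.51 | −0.03 to 0.00 |

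In one middle setting (N = 269, 25%, 12 candidates, no true predictors) the apparent AUC is 0.618, CV after one screening 0.545, and CV with in-fold screening 0.498.

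With screening done properly, the SD of the AUC is 0.042–0.074 for CV and 0.058–0.095 for the split. Setting by setting, the split's SD is 1.1 to 1.6 times as large. This is less than 1.8 because CV also carries the variability of refitting and reselecting.

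A separate Firth simulation (N = 269, 20–30% prevalence, 15 candidates, four forced, no true predictors, one screening) gave 0.53–0.54 for CV, 0.55–0.56 for the split and 0.62–0.64 for the apparent AUC.

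**The case against.** **The plan does not say that screening comes before validation.** This stands. A reader might infer from the order of the list that screening is done once and that the reported AUC will be optimistic. The list fixes no sequence, and a stability bootstrap is compatible with repeating selection in each resample. The optimism is therefore conditional.

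**The split does not throw away data.** This stands in part. A reader might infer that 30% of events are lost to the final model. Nothing says that the final model is fitted on 70%, and the other two methods can use everyone. What remains is that the split's own estimate is the noisiest of the three and adds no information.

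**Events are not declared scarce.** This stands. The text says only that a ratio is approaching a threshold, and Firth regression is the stated response.

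**The split would expose a worthless model.** This holds only if screening is confined to the training part (0.50–0.51). If screening uses all data, the split is inflated too (0.53–0.58).

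**A false claim is not assured.** This stands. A cross-validated AUC of 0.57 with about 80 events among 268 women has a 95% interval of roughly 0.49 to 0.65, which includes 0.50.

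**The consequence is small.** This stands as well. The aim is to identify predictors, and SAP-9 labels secondary outcomes exploratory.

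**Conclusion.** The point holds in two parts. The 70/30 split is explicitly planned and inefficient whatever the rest of the procedure: about 12–46 test events and an interval about 1.8 times as wide as on the full sample, for assumed prevalences of 15–40%. The second part is conditional. If screening is done once on all data, a model with no predictive value would show a cross-validated AUC of about 0.53–0.57, an apparent AUC of about 0.62 (0.60–0.67 over the settings tried) and a similarly inflated split estimate. If selection is repeated in every resample, the upward bias disappears. The plan permits either and names no headline figure.

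The documents do not support the stronger conclusion that the AUC will be optimistic, or that discrimination will be claimed where there is none. The sizes rest on assumed prevalence, number of candidates and effect sizes, and on independent predictors. The bootstrap correction and the optimism of the Youden cut-off were not simulated; for those the argument is one of principle. The consequence is confined to secondary objective 6 and the ROC figure. This is a cheap improvement and does not threaten the primary comparison.

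**What to change.** In SAP-6.1 and section 8.1 of the combined document:

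1. Delete the 70/30 partition.
2. State that the planned 10,000 bootstrap replications serve to correct optimism, and that each one repeats the whole procedure: p<0.20 screening with the a priori variables added, Firth fit, and choice of the Youden cut-off.
3. Name the optimism-corrected AUC, sensitivity and specificity as the headline results, with the apparent values shown beside them and labelled as such.
4. If 10-fold cross-validation is kept, require screening inside each fold.

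The cost is a few sentences, more computing time and, probably, a lower reported AUC. No new data are needed.

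### No calibration measure is planned for the CSD prediction model, and Firth estimation alone is unlikely to stop its predicted risks from being too extreme

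*SAP*

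**What the plan says.** SAP-6.1 states that a clinical predictive model "for CSD formation will be developed using Firth penalized logistic regression", a choice "justified by the ratio of events to variables approaching the threshold" taken from a published events-per-variable rule. It gives no threshold value, event count or number of variables. Predictors enter by "Variable selection: univariate screening ($p < 0.20$) + a priori clinical variables", and the a priori variables are not listed there.

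For validation, SAP-6.1 names a bootstrap of 10,000 replications under the label of stability, and "Internal validation: 10-fold cross-validation and 70/30 data partition". It does not say which statistic the bootstrap is to correct, or whether the screen is repeated in each resample. The cut-off is chosen by the Youden index.

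Performance is "Performance: AUC, sensitivity, specificity, positive and negative predictive values". Section 8.1 of the SAP in the combined document has "Performance: AUC, sensitivity, specificity, PPV, NPV". The performance figure for the model is a ROC curve (SAP-11; combined document, section 14).

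Neither document plans a calibration slope, calibration-in-the-large, calibration plot, Brier score or shrinkage step for this model. The Hosmer-Lemeshow test appears only for the separate adjusted CSD regression (SAP-4.3; combined document, section 6.2).

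**The concern.** A model fitted with few events per candidate variable tends to over-fit. In new women its high predicted risks are then too high and its low ones too low. Firth estimation is the only remedy named. It corrects small-sample bias in the coefficients and handles separation, but it is not designed to shrink an over-fitted model to the degree that prediction needs. It also pulls the average predicted risk slightly toward 50%.

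The planned measures cannot reveal this. If every predicted log-odds is stretched by the same positive factor, the ranking of women does not change, so AUC does not change. A re-derived Youden cut-off moves with the risks and classifies the same women as positive, so sensitivity, specificity, PPV and NPV do not change either. A model described as a clinical prediction tool could therefore be reported with a fair AUC while its risks are systematically too extreme.

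**Working it through.** **Figures in the plan.** The documents give no figure for this model. The sample size for residual myometrial thickness does reproduce: 2 × (1.96 + 0.842)² × 3.5² / 1.3² = 113.8, so 114 per group, and 114 / 0.70 = 162.9, so 163. For the model, the relevant inputs are 384 enrolled and 30% expected loss (combined document, section 11): 384 × 0.70 = 268.8, or about 268 to 269 women with 6-month data. SAP-6.1 does not say at which visit CSD is predicted; the 6-month visit is assumed.

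**Events per variable.** With 10 candidates (assumed), events per variable = 269 × prevalence / 10. For assumed CSD prevalence of 15, 20, 30, 40 and 50% this gives 4.0, 5.4, 8.1, 10.8 and 13.4. The 70/30 split leaves about 28 to 94 events for development and 12 to 40 for testing across that range.

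**Simulation A: Firth with the p < 0.20 screen.** Assumed: n = 269, 10 candidates of which 5 have a true effect, and 4 forced in. The calibration slope was measured in 20,000 new patients; a slope below 1 means that predictions are too extreme.

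| Assumed true AUC | Prevalence | Median slope | Share of trials with slope below 1 |
|---|---|---|---|
| about 0.63 | 20–50% | 0.49–0.61 | 93–99% (with the next row) |
| 0.70 | 20–50% | 0.73–0.79 | see above |
| about 0.76 | 20–50% | 0.81–0.88 | 83–86% |
| 0.86 | 37% | 0.91 | 76% |
| about 0.76, 6 candidates (269 × 0.5 / 6 = 22.4 events per variable) | 50% | 0.94 | 66% |

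Developing on 70% of the data (n = 188, AUC 0.70) gave 0.60 to 0.71.

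**What Firth adds.** Without selection, Firth improved the slope over ordinary maximum likelihood by about 0.02 to 0.06; for example 0.75 against 0.72 at 10 events per variable and AUC 0.70.

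**What the planned validation would show.** In one such scenario (AUC 0.70, prevalence 37%, with the screen) AUC was 0.719 in the development data and 0.671 in new patients. That fall would be seen. The slope of 0.78 in the same scenario would not.

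**Simulation B: weak signal, no screen.** Assumed: 268 women, 8 or 12 predictors, each with log odds ratio 0.2 per SD, which implies a true AUC of 0.65 to 0.68. Median slopes were 0.56–0.57, 0.61, 0.65–0.68 and 0.68–0.72 at prevalence 15, 20, 30 and 40%. At 20% prevalence the lowest-risk tenth was predicted at 5.0–6.5% against a true 8.4–10.0%. Mean predicted over observed risk was 1.01 to 1.09; at 20% prevalence this was about one percentage point (20.8–20.9% against 19.7–19.9%). With all 384 women the slopes were still 0.64 to 0.77.

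**Does correction work?** In simulation A's set-up, the slope was estimated by bootstrap with the screen repeated in each resample, and the coefficients were multiplied by it (60 datasets with 60 resamples each, so starting values differ by a few hundredths from the table).

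| Assumed true AUC | Prevalence 20% | Prevalence 37% |
|---|---|---|
| about 0.63 | 0.49 to 0.71 | 0.62 to 0.87 |
| 0.70 | 0.75 to 0.98 | 0.75 to 0.89 |
| about 0.76 | 0.85 to 0.97 | 0.86 to 0.98 |

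Repeating the screen matters. In a further run (268 women, 10 candidates) shrinkage brought the slopes to 0.74–0.92 with the screen repeated and 0.68–0.88 without.

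**The case against.** The strongest reply is that the documents do not promise a risk equation, a nomogram or individual risks. They name a Youden cut-off, classification measures and a ROC curve, and objective 6 in section 3.2 of the protocol is to identify predictors. Uniformly over-extreme risks leave those outputs unchanged. This stands as far as it goes. A reader might infer that wrong risks will be published, but the documents do not support that. What remains is that the SAP calls the product a clinical predictive model, and such a model should be checked for agreement between predicted and observed risk.

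A reader might also infer that nothing planned would expose over-fitting. That is too broad: the bootstrap, cross-validation and split would show it as a fall in AUC. The missing element is a calibration measure within that validation.

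Hosmer-Lemeshow does not fill the gap. It is assigned to a different model, and an in-sample fit test would not show how risks behave in new women.

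Finally, this is one part of a secondary objective, SAP-9 labels secondary outcomes exploratory, and the randomized comparison is untouched. That is correct and limits the importance of the point.

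**Conclusion.** The concern holds in a limited form. Both SAP texts omit calibration for this model and rely on Firth alone for the low ratio of events to variables. Predicted risks are expected to be too extreme, and no planned measure for the model would show it.

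The size is conditional. CSD prevalence, event count, candidate list and true signal are all assumed, and only 384, 30% and p < 0.20 come from the documents. It would be tempting to quote slopes of about 0.55 to 0.7 as the general result, but these belong to weak models with a true AUC of about 0.65 to 0.68. The defensible range is about 0.5 to 0.94. At the favourable end the problem is small, and a third of simulated trials (34%) had a slope of 1 or above.

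It would also be tempting to say that the p < 0.20 screen makes the slope worse. The simulations show no consistent direction: medians were 0.60–0.75 without the screen and 0.55–0.75 with it in one run, and 0.75 against 0.78 in another. The case for repeating the screen in each resample is that the correction is otherwise too small.

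This is a worthwhile improvement to a secondary analysis and does not threaten the trial's main conclusions.

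**What to change.** In SAP-6.1 and in section 8.1 of the combined document:

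- Add optimism-corrected calibration slope and calibration-in-the-large to the performance list, and a calibration plot beside the ROC curve.
- Estimate them in the bootstrap already planned, and state that the p < 0.20 screen is repeated in every resample.
- If predicted risks or an equation are to be reported, multiply the coefficients by the corrected slope and re-estimate the intercept so that mean predicted risk equals observed prevalence. Other shrinkage methods could serve; reporting calibration is the essential part.
- State the number of events and list the candidate variables, so that the extent of over-fitting can be judged.

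The cost is a few lines of code, one extra figure and a model that looks slightly less decisive. Correction is only partial when the signal is weak (0.49 to 0.71 in the worst case above), and the report should say so. The SAP describes itself as finalized before database lock. If lock has not occurred, this can be an amendment; otherwise it can be recorded as a justified deviation, as SAP-1 provides.

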- Independence of residuals (Durbin-Watson test)

- Absence of multicollinearity (Variance Inflation Factor < 5)
- Normality of residuals (Shapiro-Wilk on residuals)

Reported: Adjusted MD (β coefficient) with 95% CI, R^2 , adjusted R^2 , F-statistic, overall model p-value

SAP-4.3 CSD Prevalence — Analysis

Unadjusted:

- Chi-square test or Fisher's exact test (if expected cell count < 5)
- Relative Risk (RR) with 95% CI
- Absolute Risk Reduction (ARR) and Number Needed to Treat/Harm (NNT/NNH)

Adjusted:

- **Binary logistic regression** at 6–8 weeks and at 6–7 months
- Covariates: same set as RMT regression model
- Variables with $p < 0.20$ in univariate analysis AND a priori confounders (age, parity, BMI, indication) included
- Model fit: **Hosmer-Lemeshow test**
- Multicollinearity: **Variance Inflation Factors (VIF)**
- Discrimination: **Area Under the ROC Curve (AUC)**
- Results expressed as adjusted **Odds Ratios (OR)** with 95% CI

SAP-5. SECONDARY OUTCOME ANALYSES

SAP-5.1 Continuous Secondary Outcomes

- Unadjusted: t-test or Mann-Whitney U as appropriate
- Adjusted: Multiple linear regression (same covariate set)
- Results: Mean difference or median difference with 95% CI

SAP-5.2 Binary Secondary Outcomes (Complications, Transfusion)

- Unadjusted: Chi-square or Fisher's exact test
- Results: RR, ARR, NNT/NNH with 95% CI

SAP-5.3 CSD Morphological Dimensions

Analyzed within the **CSD-positive subgroup only**:

- Depth, length, width: Mann-Whitney U test
- **CSD Volume** (ellipsoid formula): Mann-Whitney U test

SAP-5.4 Repeated Measures — RMT at 6 Weeks and 6 Months

Method: Linear Mixed-Effects Model (LME)

Model structure:

- Fixed effects: treatment group, time point (6 weeks vs. 6 months), treatment × time interaction
- Random effect: participant-level intercept (accounts for within-subject correlation)
- Covariance structure: Unstructured (preferred); compound symmetry if convergence issues

Interpretation:

- Significant interaction ($p < 0.05$): treatment effect differs across time points
- Non-significant interaction: main effects interpreted independently

SAP-5.5 Symptom Outcomes (Ordinal / Binary)

- Binary symptoms (spotting, dyspareunia): Chi-square or Fisher's exact test; RR with 95% CI
- **Paired temporal evolution** (6 weeks → 6 months within each group): **McNemar's test**
- Adjusted: Binary logistic regression

SAP-5.6 Hemoglobin Variation and Blood Loss

- ΔHb : t-test or Mann-Whitney U; mean difference with 95% CI

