- **Table 5:** Safety and adverse event summary
- **Figure 2:** Bland-Altman plot for RMT reproducibility
- **Figure 3:** ROC curve for predictive model

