8.4 Measurement Reproducibility (n = 30 double-blind readings)

Variable	Method
RMT, AMT (continuous)	Intraclass Correlation Coefficient (ICC)

Variable	Method
CSD presence (categorical)	Cohen's Kappa
Temporal concordance (6w vs. 6m)	Lin's Concordance Correlation + Bland-Altman analysis

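### The planned Bland-Altman and Lin analyses of RMT reproducibility pair the 6-week scan with the 6-month scan, so true scar change is mixed with reading error; they belong on the 30 double-read examinations

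*SAP*

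**What the plan says.** The standalone SAP has a section headed "SAP-6.4 Measurement Reproducibility" with two parts.

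- The first is inter-observer concordance, by "double-blind reading (n = 30 randomly selected examinations"). RMT and AMT get one statistic: "Continuous variables (RMT, AMT): Intraclass Correlation Coefficient (ICC"). Presence of a defect gets Cohen's kappa.
- The second is introduced as "Temporal concordance of RMT measurements (6 weeks vs. 6 months"). It gets Lin's concordance correlation coefficient and "Bland-Altman analysis (mean difference and limits of agreement").

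Section 8.4 of the SAP in the combined document has the same split: ICC and kappa for the double readings, and "Lin's Concordance Correlation + Bland-Altman analysis" for the 6-week versus 6-month row only. Neither document applies Bland-Altman or Lin's coefficient to two readings of one examination.

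For reporting, SAP-11 lists Figure 2 as "Bland-Altman plot for RMT reproducibility". Section 14 of the combined document lists a Bland-Altman plot without saying what it shows, and separately lists individual RMT trajectories between the two visits.

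Elsewhere the plan treats the difference between visits as something to estimate. The primary objective (section 3.1) covers both early scar formation and how the effect holds over time. The mixed model in SAP-5.4 has fixed effects for treatment, "time point (6 weeks vs. 6 months), treatment × time interaction".

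**The concern.** Limits of agreement and Lin's coefficient describe measurement error only when the quantity measured is the same on both occasions. Here the occasions are 6–8 weeks and 6–7 months after delivery, roughly four to five and a half months apart, while the scar heals. The within-woman difference contains true change as well as reading error, and a plot of it cannot separate them. The plan cannot both model that difference as a real time effect (SAP-5.4) and display it as reproducibility (SAP-6.4 and Figure 2).

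What is at stake is how a primary endpoint's measurement quality is described. Large true change would make RMT look poorly reproducible. Little net change could be read as evidence of good reading precision when it is not a test of that. The data that do address reading error, the 30 double-blind readings, are summarised by an ICC alone. An ICC is relative to the spread between women and does not directly show bias or disagreement in millimetres. Sensitivity analysis SA-5 classifies individual women at 2.5 and 3.0 mm, so disagreement on that scale is useful to know.

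**Working it through.** **The plan's own figures.** The documents give no value for reproducibility, limits of agreement or Lin's coefficient. The two RMT inputs used below come from section 11 of the protocol: SD 3.5 mm and a difference of 1.3 mm. They reproduce its sample size: 2 × (1.96 + 0.842)² × 3.5² / 1.3² = 113.8, so 114 per group, and 114 / 0.70 = 162.9, so 163. This confirms the inputs; the point does not depend on the sample size.

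**What enters the 6-week versus 6-month difference.** Let e be the SD of a single reading's error, S the SD of true change, m the mean true change, and t₁ and t₂ the treatment effects at the two visits. With arms pooled 1:1:

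- Var(D) = 2e² + S² + (t₂ − t₁)²/4
- limits = m ± 1.96 × √Var(D)
- Lin's coefficient = 2 cov / (v₁ + v₂ + m²), where v₁ = A + e² + t₁²/4, v₂ = A + S² + e² + t₂²/4, cov = A + t₁t₂/4 and A = 3.5² − e²

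Only the term 2e² is reading error. If t₁ = t₂ the treatment term is exactly zero. If the effect grows from 0 to 1.3 mm it adds 1.3²/4 = 0.42 mm².

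**Illustration.** Assumed, not in the documents: e = 0.5 mm, m = −1 mm, S = 1 to 2 mm. Then A = 12.25 − 0.25 = 12.0.

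| Scenario | Effect at 6 weeks → 6 months (mm) | Var(D) (mm²) | Bias (mm) | Limits (mm) | Lin's coefficient |
|---|---|---|---|---|---|
| Reading error only | 0 → 0 | 0.50 | 0 | ±1.39 | 0.980 |
| No true change, constant effect | 1.3 → 1.3 | 0.50 | 0 | ±1.39 | 0.980 |
| Change −1, SD 1 | 0 → 0 | 1.50 | −1.0 | −3.40 to 1.40 | 0.906 |
| Change −1, SD 1, constant effect | 1.3 → 1.3 | 1.50 | −1.0 | −3.40 to 1.40 | 0.909 |
| Change −1, SD 1, growing effect | 0 → 1.3 | 1.92 | −1.0 | −3.72 to 1.72 | 0.891 |
| Change −1, SD 2, growing effect | 0 → 1.3 | 4.92 | −1.0 | −5.35 to 3.35 | 0.802 |

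Worked for the third row: 2 × 0.5² + 1² = 1.50; 1.96 × √1.50 = 2.40; Lin's coefficient = 24 / (12.25 + 13.25 + 1) = 0.906.

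Reading error is the same in every row. The half-width nevertheless runs from 1.39 to 4.35 mm.

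**The two sources cannot be separated from this plot.** With e = 1.0 mm and no true change, Var(D) = 2 × 1.0² = 2.00. With e = 0.5 mm and a true-change variance of 1.5 mm², Var(D) = 0.50 + 1.50 = 2.00. With no mean change in either case, both give limits of ±1.96 × √2.00 = ±2.77 mm, although the reading error differs twofold.

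**The case against.** Several points on the other side stand.

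- **The label.** Both documents call this part temporal concordance and state the pairing, and they list it apart from the inter-observer assessment. Neither says that its limits estimate reader error. But it sits under a reproducibility heading in both documents, and the figure title uses that word.
- **Which pairs Figure 2 plots.** SAP-11 does not say, and section 14 of the combined document omits the word reproducibility. The temporal pairing is the likely reading because it is the only Bland-Altman analysis specified. If the 30 double readings were meant, the plan needs the same edit.
- **The ICC.** The 30-reading ICC is a valid reproducibility measure, and SD × √(1 − ICC) gives an error in millimetres. A reader might infer that the trial would have no usable measure of RMT error; that goes too far. What is missing is a planned bias and limits of agreement in millimetres. Lin's coefficient beside an ICC on the same pairs would add little.

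Two further inferences are tempting and not supported. One is that the treatment effect as such would appear as measurement error. A constant effect cancels in the within-woman difference, and in the table it very slightly raises Lin's coefficient; only a treatment-by-time effect enters. The other is to size the problem by assuming a visit-to-visit correlation at SD 3.5 mm and setting the resulting limits against the 1.3 mm target. A correlation between observed values already contains reading error: at 0.8 with no true change, the error SD is 3.5 × √0.2 = 1.57 mm and the limits are 1.96 × √2 × 1.57 = ±4.34 mm, the same as if all of that difference were scar change. Limits for individual women are also not comparable with a difference between group means.

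**Conclusion.** The point holds as a defect in how reproducibility is assigned and labelled. Followed as written, the only Bland-Altman and Lin results would describe change plus error, under a heading and a figure title that say reproducibility, while the same plan estimates that change as real. No limits of agreement are planned for same-examination readings.

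It reaches no further than that. SAP-6.4 is descriptive, no treatment comparison uses it, and the primary analyses of RMT and defect prevalence are unaffected. It should be corrected, but it does not threaten the trial's main conclusions.

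No size can be taken from the documents. The illustrative figures rest on the assumed reading error and the assumed mean and SD of true change. The conclusion needs only that some true change in RMT can occur between the visits, which the plan itself allows for.

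**What to change.** - In SAP-6.4 and section 8.4, apply Bland-Altman to the 30 double-read examinations alongside the ICC, reporting bias and limits of agreement in millimetres with confidence intervals. Lin's coefficient on these pairs is optional.
- State in SAP-11 and section 14 that the Bland-Altman plot (Figure 2) shows those 30 paired readings.
- Take the 6-week versus 6-month comparison out of reproducibility. Label it change over time and report it by arm from the SAP-5.4 mixed model. The individual trajectories already listed in section 14 can display it.

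The cost is wording in the two SAP texts. The double readings are already planned, so no extra scan or reader is needed.
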